- Subjects will meet Rome IV criteria for functional nausea, irritable bowel syndrome, dyspepsia or functional abdominal pain as determined by a pediatric gastroenterologist
- Patients must have an intact external ear that is free of infection or severe dermatological conditions, have stable vital signs for their respective age, no history of seizures and no currently implanted electrical device

Exclusion Criteria:

- Mental retardation or pervasive developmental disorder or epilepsy
- Psychosis
- Genetic or chromosomal disorders
- Pregnancy
- Subjects who admit to substance abuse during screening
- Patients with findings of peptic ulcer disease, H.pylori gastritis, celiac disease, inflammatory bowel disease, allergic disorders, or any chronic condition or medication that may cause nausea or pain
- Patients who are treated with opioids or who had any changes in their medical regimen in the past four weeks prior to study
- Patients with a history of allergy to adhesives

Study Design Overview

Subjects will undergo medical workup per standard of care. Subjects refractory to current medical therapy may be enrolled without changes to their current medical treatment. No new pharmacological agents will be added during the 4-week study period and no changes in dosing or scheduling of current therapy will be allowed during the study period. Subjects will be screened weekly for any side effects by registered nurses who are part of the Pediatric Translational Research Unit (pTRU). All subjects will be asked to notify the PI or research team with any worsening in symptoms or side effects of therapy. If symptoms worsen or fail to improve during the study or if their clinical presentation changes in any way, subjects will have the option to drop out any time, receive standard medical therapy and appropriate referrals. If per standard of care, a subject requires a change in one or several of their regular medications during the study, they will be asked to notify the research team. To monitor this, the subjects will be inquired about their medication list and doses during their weekly visits. If the medication change is determined to potentially affect the study results, the subject may be excluded from further study as determined by the PI.

Protocol and Procedures

Pre (Baseline):

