The primary investigator, a co-investigator or research coordinator will introduce the study to eligible patients seen in the CHW Autonomic and Gastroenterology Clinic during their regularly scheduled clinic visit or while

admitted to the hospital (at the end of admit). A member of the research team will explain the details and purpose of the study during an informed consent discussion. Once the patient and caregivers have had enough time to consider participation, understand all of the risks and benefits and would like to participate, they will complete the informed consent, assent and HIPAA documents.

Medical and psychological history will be obtained to verify eligibility and screen patients for alcohol, nicotine, and drug abuse following the completion of consent/assent documents. All eligible subjects will complete the questionnaires related to demographic and the Functional Disability Inventory (FDI). This will take about 5-10 minutes total to complete.

Visit 1 and 4: Subjects will undergo blood drawn for mitochondrial bioenergetics and have EAD placed. HRV will be measured before EAD placement at visit 1 and after EAD placement at visit 4. This visit will take about 60 min. They will complete the FDI again

Visit 2; 3: EAD will be changed and a new one will be placed.

Visit 5: This visit is about 2-3 month after the last EAD has been removed. At this visit they will undergo again blood drawn for mitochondrial bioenergetics, measurement of HRV and complete FDI.

The samples will be processed and stored in the laboratory of study research team members, [name] in Health Research Center, H5720.

E. TOTAL NUMBER OF HUMAN RESEARCH PARTICIPANTS PROPOSED FOR THIS STUDY AT THIS SITE AND GLOBALLY. WHAT ARE THESE NUMBERS BASED ON?

7 patients aged 12-18 years, who are being evaluated in the Gastroenterology or FGID clinic are eligible to participate in the FGID group.

F. DRUGS OR PROCEDURES

Table 1.

	Pre	Visit 1	Visit 2	Visit 3	Visit 4	Visit 5
Screening & Consent	x					
Heart Rate Variability		x			x	x
FDI	x				x	x
EAD		x	x	x	x	
Mitochondrial bioenergetics		x			x	x

All procedures will be performed in the Children's Hospital of Wisconsin (CHW) Pediatric Translational Research Unit (pTRU).

Measurements and Data Collection

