At the time of each EAD placement, a member of the research team will inquire and document current medications and doses and if subjects experienced any side effects from the EAD during the previous week. Subjects will also be asked if they wore the device for all five days and it will be documented if the device was returned to the research team.

Demographic Information

Data will be collected as part of the clinic visit and at enrollment. This includes child's date of birth, age, sex, ethnicity, and caretaker marital status. The physician assessment will also include questions about prior medical diagnoses, co-morbid symptoms and the characteristics of pain and nausea such as timing and triggers. The FDI will be performed at visit 1; 4 and 5. This instrument has demonstrated reliability and validity and have been used for both clinical and research purposes in pediatric populations.

Medical Information

Information recorded for patients is part of clinical care and includes weight, height, vital signs, medications, gastrointestinal symptoms, early life events, family history, surgeries and other medical co-morbidities.

[figure not shown]
Heart Rate Variability

HRV reflects the variability of the R-R interval in the electrocardiogram and its frequency domains (30). HRV is an indirect measure of central autonomic control and an indicator of overall psychological well-being (31). Reductions in resting HRV reflect decreases in vagal output. The high frequency range of HRV is considered representative of vagal (parasympathetic) activity and studies show altered vagal tone as measured by HRV in subjects experiencing nausea (32). All subjects will undergo a 10 minute baseline HRV measurement (five minutes supine and 5 standing) after 10 minutes of rest. Recordings will be performed supine and standing to assess baroreflex response. HRV indices such as high and low frequency domains, low/high frequency ratio and the time domain RMSSD as a surrogate of vagal tone (30) will be analyzed using Kubios software. The RMSSD values will be the primary HRV outcome and compared to baseline (pre-EAD stimulation), post-stimulation and 2-3 month later at follow up.

We will use the following HRV collection methods; *eMotion* Faros ECG Mobile 360 and the Actiwave by CamNTech. The *eMotion* Faros will primarily used, and in the event that the faros devices are not available, the Actiwave will be available as a backup device.

eMotion Faros ECG Mobile 360

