- g. Syncope (fainting) - Rare (event rate 1% - < 5%)

Adverse effects to supporting personnel

- a. Skin piercing with percutaneous needles - Rare (event rate 1 % - < 5%)

**In our recently completed randomized trial of auricular neuro-stimulation for functional abdominal pain there were no significant or serious adverse events noted. Of 115 enrolled subjects, 10 reported side effects for following reasons, none of which were serious: ear discomfort n=6 (three active/three placebo device); adhesive allergy n=3 (one active/two placebo); syncope due to needle phobia n=1 (placebo).

Safety Monitoring Plan

All procedures will be performed by trained professionals within the standard of care under continuous medical supervision in the hospital setting (research unit). Side effects will be inquired about and documented every week during the study and at the post-study follow-up visit. If any serious harm or discomfort is identified by the subjects or the study personnel, the treatment will be discontinued. Any patient with worsening in symptoms

during the study will be able to drop out at any time and receive standard of care medical therapy. The skin of the external ear will be carefully disinfected to avoid any infection risks. Subjects will undergo vital sign screening before enrollment and vital sign assessment before EAD placement.

Safety Analysis Plan

There are no dangerous interventions related to this study, and the short study timeline allows for discontinuation of treatment when it is proven to be ineffective.

I. PROVISION FOR THE PROTECTION OF PRIVACY OF SUBJECTS AND TO MAINTAIN THE CONFIDENTIALITY OF DATA

All research projects that collect electronic data must use appropriate security measures to ensure that data is protected from theft or loss in order to prevent breaches of confidentiality. You must indicate what encryption tools (or why they are not necessary) from the options below. The IRB will not review this protocol unless you indicate the encryption tools being used to secure your research data. If you do not have encryption in place on your systems, please contact your Information Systems support to arrange for one of the encryptions options listed below.

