and labeled with the same ID and kept together with the device package. The devices will be stored in a locked room in the division of gastroenterology. The kits will be transported by a research coordinator to the TRU on the day needed. The remaining kits will be stored in the a locked room in the GI clinic, labeled with the patient's ID. Only research coordinators within the division of gastroenterology will have access to the storage room. To track use and proper disposal of the devices, subjects will be asked to return the used device the following week (at time of the next stimulator placement or follow-up visit 5 if week 4). The doctor or research coordinator will record that device was returned and dispose it properly. The research coordinator will log this data every week on each subject as devices are returned.

Data Acquisition and Analysis

Data acquisition: we will collect EKG tracing to analyze HRV, which will include heart rate, high frequency HRV, low frequency HRV and RMSSD.

For the mitochondrial bioenergetics, we will collect basal respiration, ATP production, maximal respiration, spare respiratory capacity and extracellular respiration.

We will collect cytokines at baseline, week 4 and at visit 5

Statistical Analysis

Data Management

The data gathered will be entered into REDCap data system with each ID having a unique identifier for each participant. REDCap is a secure, web-based application for building and managing online databases. All data will be de-identified and samples will only have a unique identifier that will link the unique identifier with the patient's name.

The REDCap clinical database will be maintained by the Department of Quantitative Health Sciences, at the Children's Research Institute under the direction of [name].

EKG Data, questionnaire responses, and demographic data collection forms will be coded by a member of the research team so that all protected health information is removed. This coded data will not contain any visit dates. This coded data will be analyzed by collaborators [name]. (Ohio State University) and [name] Ph.D. (University of California, Irvine) who will not be privy to any PHI. Coded data will be shared via Onedrive. Each subject's identifying number and related electronic data will be kept on a secured, MCW password-protected database that provides access only to the PI and research staff.

Missing Data Handling

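### Weekly side-effect enquiry is promised, but none is scheduled for the fourth device (25% of planned exposure) until Visit 5, about 2-3 months after its removal

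*Combined protocol and SAP*

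**What the plan says.** Two places make a general commitment. The Safety Monitoring Plan in section H says: "Side effects will be inquired about and documented every week during the study and at the post-study follow-up visit". The Study Design Overview in section D likewise has research-unit nurses screening for side effects weekly, and it places the medication check at weekly visits.

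The operating detail is under Measurements and Data Collection (section F): "At the time of each EAD placement, a member of the research team will inquire and document current medications and doses", and also "if subjects experienced any side effects from the EAD during the previous week". The same paragraph asks whether the device was worn for all five days and whether it was returned.

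Table 1 marks placements at Visits 1, 2, 3 and 4. At Visits 2 and 3, "EAD will be changed and a new one will be placed". The fourth device is placed at Visit 4. Each device runs for 5 days and the subject removes it at home.

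On Visit 5, Protocol and Procedures says: "This visit is about 2-3 month after the last EAD has been removed". The device-tracking text in section I asks for used devices back the following week, then specifies "at time of the next stimulator placement or follow-up visit 5 if week 4".

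**The concern.** An enquiry tied to the next placement works only while there is a next placement. The fourth device has none, so a team that follows the written schedule first asks about it at Visit 5. The weekly commitment is then not met for the final treatment week.

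Three things are at stake.

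- **Recording of mild events.** Several listed risks, such as dermatitis and discomfort from a dislodged electrode, arise during home wear, and the 5-minute rest after placement cannot capture them. In the sponsor's earlier trial the reported side effects were mostly ear discomfort (6 of 10) and adhesive allergy (3 of 10), none serious. Events of this kind may go unmentioned or be forgotten over 2-3 months.
- **The safety summary.** Section H summarises adverse events by assessment time, follow-up included. Week-4 events first recorded at Visit 5 may be mixed with events from the treatment-free period.
- **Wear and medication.** The same placement-linked questions cover both. The rule against medication changes applies to the 4-week period, so its last week also has no scheduled check at the time.

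The subjects are aged 12 to 18, and section G classes the research as above minimal risk.

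**Working it through.** The plan gives no figure to reproduce. The sample size of 7 was set by budget and no power calculation applies. The check sets the schedule against the commitment and counts.

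**Inputs.** 7 subjects (section D); 4 devices each (Table 1; section I); 5 days per device (section F); enquiry at each placement about the previous week (section F); Visit 5 about 2-3 months after the last removal (section D).

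**Step 1: which enquiry covers which device.**

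| Device | Placed at | First scheduled enquiry | Time from placement |
|---|---|---|---|
| 1 | Visit 1 | Visit 2 | about 7 days |
| 2 | Visit 2 | Visit 3 | about 7 days |
| 3 | Visit 3 | Visit 4 | about 7 days |
| 4 | Visit 4 | Visit 5 | 5 days of wear plus 2-3 months |

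**Step 2: share of exposure.**

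- Per subject: 4 × 5 = 20 device-days, of which 1 × 5 = 5 belong to device 4; 5/20 = 25%.
- Whole study: 7 × 4 = 28 wears, of which 7 are fourth devices; 7/28 = 25%. In device-days, 35 of 140.

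**Step 3: delay.** Taking 2-3 months as 60 to 92 days (an assumption), the first scheduled enquiry on device 4 comes 60 + 5 = 65 to 92 + 5 = 97 days after placement. Against 7 days, that is 65/7 = 9.3 to 97/7 = 13.9 times later.

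**Step 4: rough scale of events.** Neither figure estimates events missed.

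- Section H lists each risk at 1% to under 5% without naming the unit. If that rate applied per device (an assumption), the chance of at least one event of a given type among 7 fourth devices is 1 − (1 − p)^7. This is 0.068 at p = 0.01 and 0.302 at p = 0.05, so about 7% to 30%.
- In the earlier trial, 10 of 115 subjects reported a side effect, both arms combined. If the same per-subject rate held here and were spread evenly over four devices, the expected number for the fourth devices is 10/115 × 7 / 4 = 0.15.

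**Step 5: effect of one added contact.** Wears with a scheduled enquiry within about a week rise from 21 to 28 of 28, and device-days from 105 to 140 of 140.

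**The case against.** A reader might infer that there is no contact at all after Visit 4, that a quarter of exposure has no timely safety data, or that the team could not act on a skin or ear problem. The documents do not support any of these.

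- The Study Design Overview asks all subjects to tell the team about side effects.
- The EAD placement details give them a contact person to call, and same-day removal by an investigator if they cannot remove the device.
- Subjects rest in clinic after each placement, and at Visit 4 heart rate variability is also recorded after the device is on.
- Serious events go to the IRB within 24 hours.
- Side effects are asked about again at Visit 5.

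This objection stands. What is missing is a timely enquiry that the team initiates.

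A reader might also infer that the adverse-event summary has been shown to be biased low. Under-recording is a plausible direction, but nothing in the documents measures it. The expected count is small (about 0.15 under the assumptions above), the safety analysis is descriptive, and this is an exploratory pilot.

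Finally, the contradiction is partly inferred. The text says enquiry happens at each placement, not only then. Table 1 has no side-effect row at any visit, so its silence on week 4 proves little. A week-4 check could be run under the general weekly commitment. That is fair, but no section schedules one, and section I sends the week-4 device to Visit 5, which points away from an implied end-of-week visit. Spontaneous reporting also does not fulfil a commitment to ask and document every week.

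**Conclusion.** The point holds as a gap between a stated commitment and the schedule meant to deliver it. For the fourth device, 7 of 28 wears or 25% of planned exposure, no side-effect or wear enquiry is scheduled until Visit 5, about 2-3 months after removal. In the meantime the plan depends on subjects coming forward. Mild events may therefore be under-recorded, and week-4 events may be mixed with follow-up events.

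The 25% assumes that all 7 subjects receive all four devices. The 65 to 97 day delay rests on reading 2-3 months as 60 to 92 days. The number of events affected is unknown and probably small.

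This should be corrected because the plan sets the weekly standard itself and meeting it costs little. It does not mean that serious events would go unreported.

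**What to change.** Reconcile the weekly commitments in the Study Design Overview and the Safety Monitoring Plan with the visit descriptions, Table 1, Measurements and Data Collection, and the device-return text in section I.

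The simplest way is to add to Table 1 one scheduled contact about one week after Visit 4, for example a telephone call by existing research staff. It should use the same side-effect, wear and medication questions asked at Visits 2 to 4. Record the answers as the week-4 assessment, so that the summary by assessment time keeps them apart from events first arising before Visit 5. The telephone format is only a suggestion; any scheduled contact at that time would serve.

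The cost is one short call per subject, 7 in all, with no new visit or procedure and no change to treatment.

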The following encryption products employ cryptographic modules that the National Institute of Standards and Technology has certified as meeting FIPS 140-2 requirements. Children's Hospital and Health System endorsed the use of these products made to encrypt hard drives and removable media. All electronic research data must be encrypted using one or more of these products.

Please indicate which encryption tools you are using to secure your research data.

- Credent Mobile Guardian (RS, PD)
- GuardianEdge Hard Disk and GuardianEdge Removable Storage Encryption (HD, RS, PD)
- IronKey encrypted flash drives (RS)
- McAfee Endpoint Encryption (HD, RS)
- Microsoft Bitlocker (HD, RS when used with Windows 7 and FIPS compliant algorithms are enabled)
- PGP Whole Disk Encryption and PGP Portable (HD, RS)
- SafeNet Protect Disk and SafeNet Protect File (HD, RS)
- Seagate Secure Self-Encrypting Drives (HD when encryption option is enabled)
- Symantec Endpoint Encryption (HD, RS, PD)
- WinMagic SecureDoc encryption (HD) (for MCW owned computers)
- Other (add description)

Does not apply because:

- Data is de-identified – no PHI collected
- Data is stored on paper only
- Data is stored on CHW secured shared drives.
- Data is stored on MCW secured shared drives.

Key

HD = Hard Drive

RS = Removable Storage (USB flash drive, CD, etc.)

PD = Portable Device (iPod; iPhone; PDA, etc.)

Each subject will be assigned a unique identifying number. The only identifiers listed on the questionnaires, HRV, cytokines and EAD kits and data collection forms will be date of service and the subjects unique identifying number. Each subject's identifying number and related electronic data will be kept on a secured, MCW password-protected database that provides access only to the PI and research staff. Only authorized research personnel will have access to the database. A separate secure database will have the subject identification number linked to the patient's name and info. The EAD devices will be shipped directly from the manufacturer (Key Electronics) to the GI office research coordinator who will label each package of 4 EAD devices with a patient ID and serial number with a prepared sticker label. A subject folder will also be prepared

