Missing Data: Every effort will be made to avoid missing data. Using logistic regression, the pattern of missing data will be explored. Assuming the data are missing at random (MAR) multiple imputations for items will be used. Data analysis overview: Summary statistics, such as mean, median, standard deviation, range and correlation will be used as a first step to examine data. To satisfy parametric assumptions, we may perform transformations with justifications if possible and otherwise use non-parametric tests. We will use CART and biological and physiological information to identify interactions when formulating regression models. Statistical software employed for data analysis will be: Cytel StatXact, SAS version 9.4, Salford System CART for trees, SPSS Version 24. The power calculation was made using PASS 13.

Power

This is not applicable due to this being an exploratory pilot study. This study will be supported by a \$12000 from CTSI (if approved), and number of subject was based on budget.

We will similarly analyze the change in vagal tone at visit 1, visit 4 and visit 5 and the different variables of mitochondrial bioenergetics including basal respiration, ATP production, maximal respiration, spare respiratory capacity and extracellular respiration.

We will also compare cytokines at visit 1; 4 and 5 and if possible correlate the change in cytokines to changes in hfHRV and RMSSD.

J. PROVISIONS FOR MONITORING DATA TO ENSURE THE SAFETY OF SUBJECTS; AND ADDITIONAL SAFEGUARDS TO PROTECT THE RIGHTS AND WELFARE OF SUBJECTS WHO ARE LIKELY TO BE VULNERABLE

The PI will monitor the health of all patients in the study per standard clinical practice. The PI will monitor protocol adherence and supervise data collection, entry, and analysis.

K. ANTICIPATED BENEFITS ASSOCIATED WITH THE PROTOCOL TO HUMAN RESEARCH PARTICIPANTS AND SOCIETY

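### No masking of HRV readers or assay staff to visit is stated, and the plan's two sample-labelling rules conflict, in a single-arm study that rests on within-subject visit differences

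*Combined protocol and SAP*

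**What the plan says.** - **Labels on source material (section I).** Questionnaires come first in the list of items, and the identifiers on "HRV, cytokines and EAD kits and data collection forms will be date of service and the subjects unique identifying number". Mitochondrial samples are not in the list.
- **Labels on samples (section I, Data Management).** Here "samples will only have a unique identifier that will link the unique identifier with the patient's name". The same paragraph describes the identifier as one per participant.
- **Coding (section I, Data Management).** "EKG Data, questionnaire responses, and demographic data collection forms will be coded by a member of the research team". Of the result, "This coded data will not contain any visit dates". It goes to collaborators at two other universities "who will not be privy to any PHI". Blood samples and assay results are not among the items coded.
- **HRV processing (section F, Heart Rate Variability).** RMSSD is the primary HRV outcome, and the indices "will be analyzed using Kubios software". No artefact-correction setting is given.
- **Assays (sections D and F).** Blood is drawn at Visits 1, 4 and 5. Samples are processed and stored in a study team laboratory, and blood is saved for cytokine testing. No repeat or rejection rule is given.
- **Oversight (section J).** "The PI will monitor protocol adherence and supervise data collection, entry, and analysis".

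**The concern.** All 7 subjects receive the active device and know it. With no sham arm, masking can be kept only at the measurement step, by having the people who edit beats and accept assay values work without knowing the visit. The plan does not say this happens, and a label with date and subject number works against it.

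Every planned comparison is a change between visits in the same subject. If borderline beats or assay values were handled differently at Visit 1 than at Visit 4 or 5, the difference would enter the estimated change directly, and no control arm would share the error and cancel it. Section O names lower cytokines and higher hfHRV as the key findings sought and applies a 0.05 cut-off, so the direction hoped for is known to everyone involved.

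**Working it through.** **1. The texts side by side**

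| Material | Section I, identifier list | Section I, Data Management | Can the reader tell the visit? |
|---|---|---|---|
| ECG recordings | Subject number and date | Coded, no visit dates, outside analysts | Not by date once coded. Not stated whether a visit label stays or whether editing precedes coding |
| Cytokine samples | Subject number and date | Unique identifier only | Yes under the first rule. Unclear under the second |
| Mitochondrial samples | Not named | Unique identifier only | Not stated |

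A per-participant identifier cannot separate three draws from one subject. Some further mark is needed to link a result to Visit 1, 4 or 5, and the plan does not say what it is or who sees it. Section F has ECG data imported to a laptop and then into HRV software, without saying whether coding comes before that step.

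**2. How sensitive RMSSD is to one editing decision**

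The documents give no figure to reproduce, so this is for scale only.

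Inputs:
- First-visit RMSSD of the improved group in section C: 33.14 ms supine, 11.39 ms standing.
- Five minutes per posture (section F).
- Assumed heart rates: 80 bpm supine, so n = 5 × 80 = 400 intervals; 100 bpm standing, so n = 5 × 100 = 500.
- Assumed ectopic deviation d = 200 ms, with a range of 100 to 300 ms.

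An early beat followed by a compensating pause turns the intervals r, r, r, r into r, r − d, r + d, r. The successive differences are −d, +2d and −d, with sum of squares d² + 4d² + d² = 6d². Taking this as added to the record's existing variability:

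new RMSSD = √(RMSSD² + 6d²/(n − 1))

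At d = 200 ms, 6d² = 240,000:
- Supine: √(33.14² + 240,000/399) = √(1098.3 + 601.5) = 41.2 ms, a rise of 8.1 ms (+24%).
- Standing: √(11.39² + 240,000/499) = √(129.7 + 481.0) = 24.7 ms, a rise of 13.3 ms (+117%).

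Over d = 100 to 300 ms, the single-record rise is +7% to +49% supine and +39% to +206% standing.

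**3. What that does to the study's estimate**

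If it happens in one record of one subject, divide by 7:
- Supine: 8.1/7 ≈ 1.2 ms, or 3.5% of 33.14 ms.
- Standing: 13.3/7 ≈ 1.9 ms, or 17% of 11.39 ms.

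The improved group in section C rose by 59.11 − 33.14 = 26.0 ms supine and 38.40 − 11.39 = 27.0 ms standing. One beat in one subject is therefore about 4% (1.2/26.0) and 7% (1.9/27.0) of those rises. To move the mean by the full 8.1 or 13.3 ms, the same discrepancy would have to occur, in the same direction, in all seven subjects.

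**The case against.** **Date of service does not reach the named HRV analysts.** A reader might infer from the identifier list that they can tell baseline from on-treatment recordings by date. The documents do not support that: dates are removed before the ECG data leave the team, and no text says the coded files keep a visit label. This objection stands. What remains for HRV is that removing dates is a privacy step. It is not stated to be masking, and its order relative to beat editing is not given.

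**The identifier list is a privacy rule.** It limits what appears on source material and does not set out what analysts receive. That is fair, but it is one of only two labelling rules in the plan, and it conflicts with the other for cytokines.

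**The list does not name mitochondrial samples.** This stands. For them the gap is only that masking is not mentioned.

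**The RMSSD arithmetic is not a bias estimate.** Also correct. It shows sensitivity to artefact handling, which exists with or without masking. It does not show that handling would differ by visit. The heart rates and beat deviation are assumptions, the baselines come from one subgroup, and nothing comparable can be computed for the assays.

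**Some of the harm is reversible.** If the ECG tracings are kept, they can be reprocessed under masking, and saved cytokine samples can be run together. This stands as far as retention allows.

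**Oversight by the investigator proves little.** The sentence in section J does not say that the principal investigator edits beats or rejects assay values, and nothing here rests on it.

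**This is a budget-sized exploratory pilot.** That lowers the stakes, but exploratory status does not protect against directional measurement error.

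**Conclusion.** The point holds as a gap in the plan and a conflict between two of its passages. No masking of HRV readers or assay staff to visit is stated. The labelling rules disagree for cytokine samples, and under one of them visit order is visible. No artefact-correction or assay-acceptance rule is fixed in advance.

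The documents do not show that drift towards the hypothesis occurs, and +24% or +117% must not be read as the bias in the trial's result. Those are single-record figures. The matching shift in a 7-subject mean is about 1.2 ms supine and 1.9 ms standing at d = 200 ms, or 0.3 to 2.3 ms and 0.6 to 3.3 ms over d = 100 to 300 ms. They rest on the assumed heart rates and on every subject resembling the subgroup means in section C.

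The change is worth making because it is cheap and the design has no control arm to absorb measurement judgement that differs by visit.

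**What to change.** 1. Reconcile the identifier list in section I with Data Management, so that one rule governs labels on recordings and on all blood samples.
2. Give each ECG recording and each blood aliquot its own random code showing neither subject, visit nor date. One coordinator holds the key. State that coding comes before beat editing.
3. Name one Kubios artefact-correction setting in advance and apply it to every file.
4. Lock the edited RR series and the accepted assay values before the key is released.
5. Run the saved cytokine samples from all three visits together, in random position.
6. For the mitochondrial assays, use coded labels and a preset repeat and rejection rule only. The documents do not say that this material is held for batching.

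Cost: 7 × 3 = 21 recordings and 7 × 3 = 21 blood draws, so about 42 codes (more if draws are split into aliquots), a key list, and a short paragraph in section I. The main drawback is that cytokine results wait until the last Visit 5. Sample size and significance level do not change.
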